The primary goal of the proposed study is to compare TBT and matching DSTs in a large, randomized investigation in a Veteran sample via a non-inferiority design. The study will use a repeated measures RCT design to compare TBT to DSTs in 306 Veterans with PTSD, MDD, panic disorder and/or agoraphobia (PD/AG) and related symptoms of depression/anxiety and impairments. DSTs will be matched to participants' targeted diagnosis (e.g., Cognitive Processing Therapy for PTSD, CBT for MDD, and CBT for PD/AG). Assessments of disorder-specific symptomatology, as well general symptoms of the depressive/anxiety disorders and related impairments, will be used due to the transdiagnostic approach and related research aims of the proposed study. Assessments will be completed at baseline, mid-treatment, immediate post-treatment, and 6-month post-treatment follow-up. Process variables (satisfaction, attendance, discontinuation rates) also will be recorded.

Primary Aim: To examine efficacy of TBT on improving psychiatric symptomatology and related impairments in Veterans with depressive/anxiety disorders compared to DSTs.

Hypothesis: TBT will result in non-inferior improvements in psychiatric symptomatology, as assessed by the PTSD Checklist for PTSD, PHQ-9, Panic Disorder Severity Scale for PD/AG, and transdiagnostic anxiety on the State Trait Inventory for Cognitive and Somatic Anxiety and transdiagnostic impairment on the Illness Intrusiveness Rating Scale, compared to the DST control conditions.

Secondary Aim: To examine feasibility and acceptability of TBT

Hypothesis: TBT will be well tolerated by Veterans as demonstrated by improved attendance (number of weeks to complete treatment), treatment discontinuation rates (yes/no), and patient satisfaction questionnaires, as assessed by the Satisfaction with Therapy and Therapist Scale – Revised, as compared to the DSTs.

B. BACKGROUND AND SIGNIFICANCE

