For all study outcomes (ADIS-5, IIRS, PCL-5, PDSS, PHQ-9, and STICSA), Veterans will be randomly assigned (1:1) to the TBT and specific DST conditions. The power analysis was calculated to be powered at 80% with a Bonferroni-corrected 1-tailed $\alpha = .006$ (.025/4 primary outcomes) to detect non-inferiority for TBT in comparison to the aggregated DST effect. Meta-analyses for CBT for MDD, CPT for PTSD, and CBT for PD/AG reveal large treatment effects (CBT for MDD bias-adjusted $g = .53$; Cuijpers et al., 2013; CPT for PTSD in military personnel $g = 1.33$; CBT for PD $g = 0.35$; Hofmann & Smits, 2008). Thus, the average effect size for DSTs was expected to range from small-to-medium to large. A power analysis was conducted using procedures recommended by Chow, Shao, and Wang (2017), Flight and Julious (2014), and Julious (2004) as well as recommendations by the United States Food and Drug Administration and the European Medical Association (Food and Drug Administration, 2017). An important topic in non-inferiority designs is selection of the “appropriate” prespecified non-inferiority limit. Current best practice involves selecting a non-inferiority margin that is not greater than the smallest effect size expected for the DSTs in comparison to a control condition. As a tradeoff between sample size needs and feasibility of recruitment, we conducted power analysis setting the non-inferiority margin to 0.5, indicating that we would consider TBT non-inferior to the DSTs if TBT were to perform less than half a standard deviation worse than the DSTs. We set the expected group different to 0.3 given our pilot data demonstrating that TBT outperforms DSTs by this margin across primary outcome variables. Using procedures recommended by Chow, Shao, and Wang (2017) for non-inferiority designs, which utilize the pre-specified non-inferiority margin (here prespecified as $\Delta d = 0.5$) and the estimated effect in the active comparison treatment ($d = 0.3$), we determined that 144 participants (72 per cell) would be needed. However, this does not account for potential attrition or for potential design effect issues involving therapist effects or for potential missing data related to telehealth delivery of services. To account for possible attrition and missing data as well as the potential influence of design effects, we increased the sample size to 306 participants based on the data available to date. Based on pilot data, we expect to find large within-person effects ($d \geq .80$) for TBT, indicating 4/5ths of a SD reduction in each of the primary outcome measures. This sample size would leave us powered to detect small-to-medium within-person effect sizes.

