The continuous measures included measures of disorder severity scales (ADIS-5), disorder-specific symptomatology (PCL-5, PDSS, PHQ-9, and STICSA), general related symptomatology (STISCA), and quality of life and impairment (IIRS). Of these variables, the PCL-5, PDSS, PHQ-9, and STICSA are the primary outcomes of interest. All other analyses will be conducted in an exploratory fashion to inform future studies and compare findings to previous studies ([name], 2014; [name] et al., 2017; 2019). Parameter estimates to calculate the effect size difference will be arrived at using three-level (measurement occasions nested within participants nested within assigned treatment condition) generalized mixed-effects regression models (MRM). MRM is a method of repeated measures analyses that allows for modeling of continuous and categorical independent and dependent variables and for appropriate modeling of covariance structures when observations are correlated across time and/or across condition. This analytic approach fully captures variability in outcomes across multiple follow-up assessments and accounts for any potential effect of the group to which a participant is assigned and is thus preferred over methods that collapse data over time. We will calculate between-group treatment differences as Cohen's d, based on the effect of treatment condition on the intercept parameter when the model is centered on post-intervention and on the effect of treatment condition on the intercept parameter when the model is centered on month 6. We prespecified the non-inferiority margin (d) to be 0 (indicating we expected TBT to be at least equivalent to the aggregate DST effect) and the one-sided CI for our four primary analyses at $\alpha = .006$. In the primary analyses of outcome variables, we will covary for the baseline value of the variable of interest. We also will include the linear effect of time as well as a time by condition interaction effect to determine whether treatment differences (or lack thereof) were stable from post-intervention through the follow-up. Additional covariates (e.g. age, number of psychiatric comorbidities, race, sex, combat theatre, number of treatment sessions, specific DST received) will be added to the model to adjust for putative confounding variables. Effect size CIs that do not contain 0 provide evidence in support of noninferiority for TBT. The primary outcome time point is at the end of the active treatment phase and the secondary time point is at the end of the naturalistic 6-month follow-up period. Further, within-subject effect sizes from baseline to post-intervention and to 6-month follow-up also will be calculated within the TBT condition to quantify TBT-specific reductions in symptoms. These analyses will be probed to examine potential therapist effects. First, design effects will be calculated for the primary outcome variables. Design effects > 2 are often used as a heuristic to judge when these effects can be problematic.

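### The fixed one-sided .006 on each of four primary outcomes is valid, but Holm is never less powerful at the same familywise .025; the 80% should be labelled per-outcome power

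*Combined protocol and SAP*

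**What the plan says.** The section on sample size determination states "The power analysis was calculated to be powered at 80" percent, at a "Bonferroni-corrected 1-tailed" alpha of .006, which it derives as .025 divided by four primary outcomes. The same section fixes the margin with "we conducted power analysis setting the non-inferiority margin to 0.5" and the assumed truth with "We set the expected group different to 0.3 given our pilot data demonstrating that TBT outperforms DSTs by this margin". It arrives at 144 participants (72 per cell) and raises this to 306, which is 153 per arm at 1:1.

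The efficacy analysis section for the primary aim names the PCL-5, PDSS, PHQ-9 and STICSA as primary and sets "the one-sided CI for our four primary analyses" at .006. It plans no step-down or other sequential procedure. It puts the non-inferiority margin at 0, not 0.5.

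The primary-aim hypothesis says "TBT will result in non-inferior improvements in psychiatric symptomatology" and then lists five measures: those four and the IIRS. The randomization section gives 108 per arm.

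Nowhere do the documents say whether success needs one, some or all of the outcomes, or whether 80% refers to one outcome or to several together.

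**The concern.** A fixed split of .025 over four outcomes protects against any false claim when each outcome may succeed alone. The plan does not say that this is the claim structure, and under either natural structure a test at least as powerful is available:

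- **Each scale is its own claim.** Holm controls the same familywise .025 and never rejects less than Bonferroni.
- **All four scales must succeed.** No split is needed; testing each at one-sided .025 already controls the error of the joint claim.

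At stake is the chance of missing non-inferiority on a scale where an equally strict procedure would have shown it. A second issue is one of reading: 80% computed at a per-outcome alpha is per-outcome power, and the text does not say so.

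**Working it through.** **Inputs from the documents.** One-sided alpha .006 per outcome (.025/4 = .00625 exactly); power 80%; four primary outcomes; margin 0.5 (sample size) or 0 (analysis); TBT better by 0.3; 72, 108 or 153 per arm. **Assumed:** SD 1, equal correlation between outcomes of 0, 0.3, 0.5 or 0.7, the same true effect on all four, and no loss of participants.

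**Step 1: the plan's own sample size.** n per arm = 2(z_alpha + z_power)² / D², where D is the distance from the true difference to the margin. Here z(.994) + z(.80) = 2.512 + 0.842 = 3.354, and 2 × 3.354² = 22.50.

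- TBT better by 0.3, D = 0.5 + 0.3 = 0.8: 22.50/0.64 = 35.1, so 36 per arm (72 in total).
- No difference, D = 0.5: 22.50/0.25 = 90 per arm (180 in total).
- TBT worse by 0.3, D = 0.2: 22.50/0.04 = 562.4, so 563 per arm (1126 in total).

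None gives 72 per arm; 72 appears only as a total, in the first case. Per-outcome power at 72 per arm is Φ(D√(72/2) − 2.512), which gives Φ(4.8 − 2.512) = 98.9%, Φ(3.0 − 2.512) = 68.7% and Φ(1.2 − 2.512) = 9.5%. The stated 80% is therefore not reproduced, and any figure built on it is conditional.

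**Step 2: joint power.** Four equicorrelated z-statistics with mean D√(n/2) were simulated, with 1,000,000 draws per case (600,000 for the 108-per-arm row). Fixed rule: every p ≤ .006. Holm: ordered p-values against .025/4, .025/3, .025/2 and .025. Conjunctive rule: every p ≤ .025. Ranges run over correlation 0 to 0.7.

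| Case | Per-outcome power at .006 | All four, fixed .006 | All four, Holm | All four, .025 each |
|---|---|---|---|---|
| 80% at face value (mean 3.354) | 80% | 41-62% | 70-80% | 71-82% |
| 72 per arm, margin 0.5, TBT +0.3 | 98.9% | 96-97% | 99% | 99% |
| 72 per arm, margin 0.5, no difference | 68.7% | 22-47% | 50-67% | 53-70% |
| 108 per arm, margin 0.5, no difference | 88% | 59-74% | 83-88% | 84-89% |
| 153 per arm, margin 0.5, no difference | 97% | 88-92% | 97% | 97-98% |
| 153 per arm, margin 0.5, TBT +0.3 | 100% | 100% | 100% | 100% |
| 153 per arm, margin 0, TBT +0.3 | 54% | 9-31% | 28-51% | 31-54% |

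As a check on the first row, under independence 0.80⁴ = 0.41. In that row Holm raises average per-outcome power from 80% to 87-90%.

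**Step 3: error rate.** Holm's simulated familywise error was .0249 with all four nulls true and outcomes independent, and .025 with three real effects and one null. Holm's first step is the Bonferroni step, so the chance of at least one success is unchanged apart from the rounding of .00625 to .006.

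**The case against.** The fixed rule is prespecified, valid under any correlation, and the same in the sample-size and analysis sections. It also suits a plan that decides by confidence intervals, because four fixed-level bounds are simultaneous and easy to report. All of that stands, and preferring Holm is a matter of efficiency.

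A reader might infer that the plan wastes power and that 80% overstates the chance of supporting the hypothesis. The documents do not support this as a general statement. The 41-62% comes from a mean of 3.354 that is solved backwards from 80% at .006. On the sample-size section's own favourable inputs, all-four power is 96-97% under the existing rule, already above 80%. At 153 per arm on those inputs Holm adds nothing.

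A reader might also infer that the hypothesis requires success on every scale. No such rule is stated, and 80% is never presented as joint power. If all scales were required, .025 each would be the right test and would do at least as well as Holm.

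The favourable case is still not secure. The sample-size section also describes the 0.3 as "the estimated effect in the active comparison treatment ($d = 0.3"), the analysis section uses a margin of 0, and the arm size is given two ways. The less favourable rows therefore cannot be set aside.

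**Conclusion.** The point holds as a cheap improvement. The planned test is valid but avoidably no better than, and often weaker than, a step-down test with the same familywise .025. The increase in all-four power runs from nothing (153 per arm, margin 0.5, TBT better by 0.3), through 2 to 4 points (the same inputs at 72 per arm), to roughly 18 to 29 points if per-outcome power really is 80%, and about 19 to 21 points with margin 0 and 153 per arm. These figures rest on assumed correlations of 0 to 0.7, equal effects across outcomes and no attrition or therapist clustering. No single gain can be quoted while the margin, the arm size and the number of outcomes remain inconsistent.

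**What to change.** In the efficacy analysis section for the primary aim:

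1. State the success rule; that choice belongs to the sponsor.
2. If each scale is its own claim, test the four primary outcomes with Holm, comparing the ordered one-sided p-values with .025/4, .025/3, .025/2 and .025. Let the adjusted p-values govern the decision, and still report the fixed-level intervals.
3. If all four must succeed, test each at one-sided .025 with no split.

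In the sample-size section, describe the 80% as per-outcome power. Reconcile the margin (0.5 or 0), the arm size (108 or 153) and the number of outcomes (four, or five with the IIRS). Only then add joint power over a stated range of correlations.

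The cost is a wording change, to be made before unblinded data are seen, with no more participants and no change in familywise error. The downside is that intervals matching Holm's decisions are less simple than four fixed-level ones, so the text must say that the adjusted p-values decide when the two differ.

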Participants who meet inclusion/exclusion criteria will be randomized into a study condition and will be assigned to a project therapist. Because most VAMC patients who meet study criteria likely will present with multiple depressive/anxiety disorders (Brown et al., 2001), principal diagnosis, or the most impairing of the diagnosable disorders, will be used to inform randomization. Principal diagnosis will be determined via diagnostic severity scores in the Anxiety Disorders Interview Schedule-5 (ADIS-5) (Brown, 2014). To balance diagnoses across the two conditions, a stratified random assignment based on principal diagnosis will be used (MDD, PTSD, and PD/AG) ([name], 2015). Based on referrals to the PI's CDA, it is expected that at least 45% of the recruited Veterans will have served in OEF/OIF and $\geq 50\%$ will be representative of minority groups.

Eligible VAMC patients will be randomized into one of two treatment conditions: TBT or DSTs. Both treatment conditions will include 12 weekly 45- to 60-minute treatment sessions. Both treatment conditions will be delivered either in-person and via VA-approved telehealth technologies, based upon the preference of the participant. The general format of sessions will involve: 1) brief check-in; 2) review of materials from previous sessions; 3) review of homework assignments; 4) overview of new materials and in-session exercises; and 5) assignment of homework for next session. Attendance and homework completion will be recorded.

Randomization Procedures

Participants will be randomly assigned (1:1) to one of the two study arms ($n = 108$ per arm) using a permuted block randomization procedure. Randomization will be stratified by diagnostic group (PTSD, PD/AG, MDD) and block size will be varied to minimize the likelihood of unmasking. After determining eligibility and completing consent and baseline assessment materials, enrolled participants will be assigned to their treatment condition by the Research Project Therapist/Coordinator using a computer-generated randomization scheme. Once a participant is randomized, they will be included in the modified intent-to-treat (MITT) analysis. The Research Project Therapy/Coordinator and the statistical analyst in charge of randomization ([name]) will be the only

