1983). The IIRS has been shown to have strong psychometric properties in the previous literature in participants with physical and/or emotional health concerns (Devins, 2010), and has been used in previous TBT studies ([name], 2014; [name] et al., 2017; 2018).

Intolerance of Uncertainty Scale Short Form (IUS-12). The IUS-12 is a 12-items scale for measuring trait intolerance of uncertainty (Carleton, Norton, & Asmundson, 2007). In other words, it is used for assessing the degree to which individuals are able to tolerate the uncertainty of ambiguous situations, the cognitive and behavioral responses to uncertainty, perceived implications of uncertainty, and attempts to control the future.

Medical Outcomes Study Social Support Survey Form (MOSSS). The MOSSS is a widely used 19-item self-report measure designed to assess social support. Responses are given on a 6-point scale ranging from 1-6 with greater scores indicating greater support. The MOSSS has been shown to be an accurate measure of social support in veteran samples with mental health issues (Jakupcak et al, 2011).

Panic Disorder Severity Scale (PDSS). The PDSS is a 7-item scale for the frequency and distress of panic attacks and related symptoms (Shear et al., 1997). The scale has demonstrated good internal consistency, test-retest reliability, and sensitivity to change during the course of treatment (Houck et al., 2002). *The PDSS will be used to assess symptoms of PD/AG.*

Perseverative Thinking Questionnaire (PTQ). The PTQ is a 15-item measure of repetitive negative thinking (Ehring et al. 2011). Perseverative thinking is repetitive, negative thoughts that persist intrusive to the point of being seen as unproductive to the individual. The thought process and the individual seeing the thoughts as dysfunctional can also characterize this thinking. Items are measured on a 5-point Likert-type scale of Never (0) to Almost Always (4). These 15 questions address repetitiveness, intrusiveness, difficulty to disengage, unproductiveness, and capturing mental capacity. Studies have shown that the PTQ hold convergent validity, predictive validity, internal consistency, and test-retest reliability.

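### The disorder-specific primary scales are compared only across all diagnoses, so the planned tests do not show whether TBT matches each DST on the disorder it was chosen for

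*Combined protocol and SAP*

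**What the plan says.** All references are to the combined protocol and SAP, part D.

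- **Comparison.** Sample Size Determination for Proposed Analyses sets the power "to detect non-inferiority for TBT in comparison to the aggregated DST effect". Missing Data defines the analysis set as everyone randomized.
- **Outcomes.** Efficacy Measures Analyses (Primary Aim): "Of these variables, the PCL-5, PDSS, PHQ-9, and STICSA are the primary outcomes of interest". Everything else is exploratory. The measure descriptions tie scales to disorders, for example "The PDSS will be used to assess symptoms of PD/AG", and likewise the PHQ-9 to MDD. The primary hypothesis pairs the PTSD Checklist with PTSD. None of these passages restricts a scale's analysis to the patients with that disorder.
- **Matching and strata.** DSTs Control Condition Matching and Assignment gives each DST patient the therapy for the most severe diagnosis. Randomization Procedures: "Randomization will be stratified by diagnostic group (PTSD, PD/AG, MDD").
- **Use of diagnosis in the model.** The DST received appears only in a list of possible adjustment covariates. No treatment-by-diagnosis term is mentioned.
- **Test level and margin.** The level is a "Bonferroni-corrected 1-tailed $\alpha = .006$ (.025/4 primary outcomes"). The sample size section states "we conducted power analysis setting the non-inferiority margin to 0.5". The efficacy section states "We prespecified the non-inferiority margin (d) to be 0 (indicating we expected TBT to be at least equivalent to the aggregate DST effect") and takes a confidence interval that excludes 0 as support for non-inferiority.

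**The concern.** The trial matches the control therapy to the diagnosis so that TBT is compared with the therapy a patient would otherwise receive for that disorder. The natural question is then whether TBT does as well on PTSD symptoms in PTSD patients, on panic symptoms in PD/AG patients and on depression in MDD patients. The planned tests answer a different one: whether the two arms differ on each scale in a mix of patients, many of whom were not treated for the disorder that the scale measures. If the therapies differ mainly on the target disorder, the other patients dilute that difference. In a non-inferiority test, dilution works in favour of the new treatment.

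The protocol's own rationale makes such a pattern plausible. Its background section describes most DSTs as narrowly aimed at the symptoms of one disorder, and it expects TBT to cover comorbid symptoms better. A DST advantage on the target scale, with parity or a TBT advantage elsewhere, is what pooling would hide. A pooled pass could then be read as showing that TBT matches, say, CPT for PTSD, which the planned tests cannot show.

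**Working it through.** **Inputs from the documents.** One-sided alpha .006; 80% power; margin M = 0.5 SD (sample size section) or 0 (efficacy section); 306 participants randomized 1:1, so n = 153 per arm; expected TBT advantage 0.3 SD.

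**Assumptions, because the documents give no figure.** Stratum share w = 1/3 (range 20% to 60%); SD of 1 in every stratum; effect e of TBT on a scale in patients with another principal diagnosis (0 as the base case, then varied); loss to follow-up, with pilot treatment completion of 80.0% and 72.4% as a stand-in: 153 × 0.800 = 122 and 153 × 0.724 = 111 per arm.

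**1. The plan's own sample size.** n per arm = 2(z.994 + z.80)² / (M + TBT advantage)², with 2 × (2.512 + 0.842)² = 22.50 and M = 0.5.
- TBT 0.3 better: 22.50/0.64, rounded up to 36 per arm (72 in total).
- No difference: 22.50/0.25 = 90 per arm.
- TBT 0.3 worse: 22.50/0.04, rounded up to 563 per arm.

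The stated 144 (72 per cell) does not come out of these inputs. That is a separate matter. What follows uses 306.

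**2. Pooled difference on one scale.** With TBT 0.5 SD worse on the patient's own target scale: δ = w × (−0.5) + (1 − w) × e. Base case: δ = −0.5/3 = −0.167.

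**3. Chance of passing.** P = Φ((δ + M)/√(2/n) − 2.512). At n = 153, √(2/153) = 0.1143. Base case with M = 0.5: 0.333/0.1143 = 2.916, and Φ(2.916 − 2.512) = 65.7%.

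| Scenario (own-target deficit 0.5 SD) | δ | M | n per arm | Pass, per scale |
|---|---|---|---|---|
| Equal strata, e = 0 | −0.167 | 0.5 | 153 | 65.7% |
| Same | −0.167 | 0.5 | 122 | 53.6% |
| Same | −0.167 | 0.5 | 111 | 48.8% |
| Share 20%, e = 0 | −0.10 | 0.5 | 153 | 83.8% |
| Share 50%, e = 0 | −0.25 | 0.5 | 153 | 37.2% |
| Share 60%, e = 0 | −0.30 | 0.5 | 153 | 22.3% |
| Equal strata, e = −0.25 (half the deficit spreads) | −0.333 | 0.5 | 153 | 14.6% |
| Equal strata, e = +0.3 | +0.033 | 0.5 | 153 | 98.4% |
| Equal strata, e = 0 | −0.167 | 0 | 153 | 0.004% |
| Equal strata, e = +0.3 | +0.033 | 0 | 153 | 1.3% |

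For M = 0 the efficacy section gives no direction for the interval. It is read here as a lower bound above 0 in favour of TBT.

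**4. All three scales together.** In the base case at 153 per arm and M = 0.5, all three pass 28% of the time if they are independent (0.657³ = 0.284), and 47% at a between-scale correlation of 0.7 (simulation).

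**5. Break-even.** With equal strata and e = 0, the own-target deficit must reach 0.5 × 3 = 1.5 SD before the pooled deficit equals 0.5.

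**6. A matched-target outcome** (each patient scored on the scale of the principal diagnosis; M = 0.5). A true 0.5 SD deficit passes with probability Φ(−2.512) = 0.6%. With no true difference, power is Φ(0.5/0.1143 − 2.512) = 96.9% at 153 per arm and 88.7% at 111.

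**7. One stratum alone.** 306/6 = 51 per arm. The 95% half-width is 1.96 × √(2/51) = 0.39 SD. Power with no difference is Φ(0.5/√(2/51) − 2.512) = 50.5%.

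**The case against.** The strongest reply is that the plan states its estimand and tests it correctly. The target is TBT against the aggregate DST effect. In the base case the true aggregate difference is 0.17 SD, inside a 0.5 margin, so a pass is the right answer to the question asked. This stands. A reader might set 66% beside the nominal 0.6% and infer an inflated type I error. The documents do not support that: the 0.6% would apply to an own-disorder estimand that the plan does not declare.

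A reader might also infer that a full-margin deficit would pass under this plan as it stands. That holds only for the 0.5 margin. Under the margin of 0 in the efficacy section, being a full margin worse has no meaning and the base case almost never passes.

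Third, zero effect outside the target stratum is an extreme case. Procedures expects most patients to have several of these disorders, all participants in both pilots did, and the DSTs were chosen partly because they improve comorbid symptoms. Spill-over is therefore plausible, and it lowers the pass rate sharply. Stratum shares are not stated, and the protocol expects them to vary.

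It is also tempting to add that between-diagnosis spread inflates the SD behind d. The plan does not say which SD standardises d, so that cannot be claimed.

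Finally, ADIS-5 severity is among the planned continuous outcomes. It is exploratory, however, and no own-diagnosis contrast is specified for it, so it does not fill the gap.

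**Conclusion.** The gap is real: neither stated margin rule gives an estimate of TBT against the matched DST on the disorder being treated. How much this matters depends on assumptions. With the 0.5 margin, equal strata and no spill-over, an own-target deficit of 0.5 SD passes each scale somewhat more often than not at full enrolment and about half the time at pilot-level completion. The range is wide once stratum share and spill-over vary, and all three scales passing together is less likely than not. With a margin of 0 the illustration disappears, but the missing estimate remains. The defect is one of what the trial can claim, not of error control in the declared tests. It should be corrected because correction needs no new data.

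**What to change.** 1. Reconcile the margin between the sample size and efficacy sections first. The supportive analysis below needs one margin to be judged against.
2. Keep the pooled primary tests as they are.
3. Pre-specify one supportive matched-target analysis in all randomized participants: PCL-5 for the PTSD stratum, PDSS for PD/AG, PHQ-9 for MDD. Standardise each by a within-stratum baseline SD named in advance, and use the same model. Report the difference with its confidence interval against the reconciled margin. If that margin is 0.5, state openly that it exceeds the g = 0.35 which the sample size section cites for CBT for PD, although the same section says a margin should not exceed the smallest expected DST effect.
4. Report each scale's difference with its interval in its own stratum, for estimation only, and the treatment-by-stratum interaction.
5. Limit disorder-level claims to what items 3 and 4 support.

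Cost: SAP wording and a small amount of extra modelling on outcomes already collected and strata already randomized. There is no change to sample size. The downside is that a pooled non-inferiority result may have to be qualified, and that the stratum intervals will be too wide to settle any single disorder.

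### The plan prespecifies two different non-inferiority margins for the same primary test: 0.5 SD in the sample size section and 0 in the analysis section

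*Combined protocol and SAP*

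**What the plan says.** Sample Size Determination for Proposed Analyses describes the aim as "to detect non-inferiority for TBT in comparison to the aggregated DST effect". It reports best practice as "selecting a non-inferiority margin that is not greater than the smallest effect size expected for the DSTs in comparison to a control condition". The meta-analytic effects it lists are 0.53 for depression, 1.33 for PTSD and, for panic disorder, "CBT for PD $g = 0.35". It then sets the margin: "As a tradeoff between sample size needs and feasibility of recruitment, we conducted power analysis setting the non-inferiority margin to 0.5". The same paragraph calls 0.5 prespecified and explains it as TBT doing less than half a standard deviation worse than the DSTs. From this margin, 80% power, one-sided alpha .006 and a figure of 0.3, it concludes that "144 participants (72 per cell) would be needed", and then raises the total to 306.

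The 0.3 is described in two ways. It comes from pilot data in which "TBT outperforms DSTs by this margin across primary outcome variables". A sentence later it is "the estimated effect in the active comparison treatment ($d = 0.3").

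Efficacy Measures Analyses (Primary Aim) gives a different margin: "We prespecified the non-inferiority margin (d) to be 0". It keeps the one-sided alpha of .006 for the four primary outcomes and takes intervals that exclude 0 as support for non-inferiority. It states neither a sign convention for d nor the side on which 0 must be excluded.

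**The concern.** A non-inferiority conclusion is defined by its margin, and here two values are each called prespecified for the same four outcomes. An interval that must lie wholly above 0 in TBT's favour is a superiority test, whereas the objective and hypothesis describe non-inferiority. An analyst could follow either section and claim to have followed the plan, so the choice stays open until the data are seen. The power statement belongs to only one of the two rules.

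The second issue is the size of the 0.5. It is 0.15 SD above the smallest effect in the plan's own list, and the plan gives no clinical or effect-preservation argument for it.

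**Working it through.** **Inputs.** One-sided alpha .006, 80% power, margins 0.5 and 0, difference 0.3, 72 per cell and a total of 306 come from the two sections above. At 1:1 allocation, 306 gives 153 per arm. The scale is standardised (SD = 1), and d is taken as positive when TBT is better. z(.994) = 2.512; z(.80) = 0.842; sum 3.354.

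**The plan's own figure.** n per arm = 2 × (3.354 / (margin + d))².
- Margin 0.5, d = +0.3: 2 × (3.354/0.8)² = 35.2, so 36.
- Margin 0.5, d = 0: 2 × (3.354/0.5)² = 90.0, so 90.
- Margin 0.5, d = -0.3: 2 × (3.354/0.2)² = 562.5, so 563.

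None of these gives 72 per cell. The first gives 72 in total, so a total may have been recorded as a per-cell number, but that is an inference.

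**Do the two rules disagree on plausible results?** Half-width = 2.512 × √(2/n).
- At n = 153: 2.512 × √(2/153) = 0.287. An observed d of -0.15 has lower limit -0.15 - 0.287 = -0.437, which is above -0.5 and below 0.
- The 0.5 rule is met when d exceeds -(0.5 - 0.287) = -0.213. The 0 rule is met when d exceeds +0.287. Every observed d between these values passes one rule and fails the other.

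**Power under margin 0.** Power = Φ((d + margin) × √(n/2) - 2.512), unadjusted. The enrolment allowance is 306/144 = 2.125. If it is entirely used up by attrition, missing data and design effect, 153/2.125 = 72 per arm remain.
- d = +0.3, n = 153: Φ(2.624 - 2.512) = 0.54.
- d = +0.3, n = 72: Φ(1.800 - 2.512) = 0.24.
- d = 0, any n: Φ(-2.512) = 0.006.
- 80% power at d = +0.3 needs 2 × (3.354/0.3)² = 250 per arm.

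**Effect of baseline adjustment.** The analysis covaries the baseline value. With d on the unadjusted SD, the first term is divided by √(1 - r²). The documents give no baseline-outcome correlation r; 0.4 to 0.7 is an assumption.
- n = 153: Φ(2.624/0.917 - 2.512) = 0.64 to Φ(2.624/0.714 - 2.512) = 0.88.
- n = 72: Φ(1.800/0.917 - 2.512) = 0.29 to Φ(1.800/0.714 - 2.512) = 0.50.

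**The quoted ceiling.** The smallest listed effect is 0.35, and 0.5 - 0.35 = 0.15. The simple mean of the three listed effects is (0.53 + 1.33 + 0.35)/3 = 0.74.

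**The case against.** The plan does not hide its choice. It reports best practice and then says that it is trading it off, so the reader is warned. The planned comparison is with the pooled DST arm, whose simple mean listed effect is 0.74, well above 0.5. The 0 in the analysis section is stricter than 0.5, so following it cannot produce a lax non-inferiority claim. Its explanatory parenthesis, which speaks of an expectation that TBT does at least as well, suggests that the sponsor may have been describing the expected difference rather than a margin. Finally, baseline adjustment could bring power at margin 0 above 80% if the correlation is high and nothing is lost.

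Much of this stands, but it does not remove the contradiction. If 0 was meant as an expectation, the interval rule in the same section still tests against 0. If 0 was meant as the margin, the sample size was derived for another test. The plan computes no pooled effect and does not use one to justify 0.5.

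Three stronger readings are tempting, and the documents do not support them.
- A reader might infer that 0.5 breaks a binding rule and that the margin must be at most 0.35 on every outcome. The text describes best practice and departs from it openly. It does not establish what 0.35 was compared with, or that a panic disorder figure applies to the pooled DST arm on all four scales.
- A reader might infer that feasibility cannot explain 0.5, because the formula above gives 2 × (3.354/0.65)², or 54 per arm, at margin 0.35 and d = +0.3, below the stated 72. That formula does not reproduce 72. Scaling 72 by (0.8/0.65)² gives about 109 per arm, or about 464 in total after the 2.125 allowance, which exceeds 306.
- A reader might apply the 2.125 allowance to the 108 per arm given under Randomization Procedures. The allowance is derived from 306, not from 216, so those figures would have no basis.

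**Conclusion.** The decision rule for the primary outcomes is wrong as written: two prespecified margins, 0.5 and 0, with no reconciliation and no stated direction for the second. At 153 per arm, unadjusted and without losses, the two rules give opposite answers for any observed d from about -0.21 to +0.29.

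The 80% power claim does not carry over to margin 0. At a true advantage of 0.3, unadjusted power is about 54% before losses and 24% after the full allowance. With an assumed baseline correlation of 0.4 to 0.7 the ranges are 64% to 88% and 29% to 50%. So a shortfall is clear without adjustment or with the full allowance, but not in every case. If the treatments are equal, the chance of success at margin 0 is 0.6% at any sample size.

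That 0.5 exceeds the quoted ceiling, with feasibility as the only reason, is a real but secondary point. It matters only if 0.5 governs.

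**What to change.** Before analysis, put one margin and one directional rule in both sections, for example: *TBT is non-inferior on an outcome if the lower one-sided 99.4% confidence limit of d (TBT minus DST, positive favouring TBT) is above minus the margin.*

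- Choose a margin within the quoted ceiling and say what the 0.35 was compared with, or state that the margin exceeds the ceiling and justify it on grounds other than feasibility. If 0 is kept, call the test superiority.
- Restate power for the chosen margin at 153 per arm, at +0.3 and at zero difference, and say whether baseline adjustment is assumed. Reconcile the 108 per arm under Randomization Procedures with 306.
- Say whether 0.3 is TBT's advantage or the comparator's effect. If it is the latter, the plan states no true difference.

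The cost is protocol and SAP wording, and a less favourable power statement. For illustration, unadjusted and at zero difference, moving from 0.5 to 0.35 lowers power from 97% to 71% at 153 per arm before losses, and from 69% to 34% at 72 per arm. At +0.3, margin 0.35 still gives 99.9% and 92%. A margin of 0.35 would also be looser than the 0 now in the analysis section, so the change should be stated openly.
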